3.2 Study Population

A total of 20 MSI-H/dMMR, non-CRC patients with an advanced solid cancer (primary focus will be gastric and gynecological cancers) diagnosis and a history of previous treatment will be included in this study. In the recruitment phase, we will work with investigators at major cancer centers in Taiwan to proactively identify eligible patients. MSI-H/dMMR status can be determined by any specific assays (IHC- or PCR-based) that are used in routine clinical practice. In addition, patients tested with next-generation sequencing (NGS) with a derived MSI-H status across all solid tumor types will also be considered to enrich the study population. The recruitment phase will be closed once 20 non-CRC patients are consented and included in the registry. It is estimated that at least

Protocol/Amendment No.: 1.1 (14 Sep 2019)

VEAP ID NO: 8439

Epidemiology No.: EP05026.058

2 years are needed for the patient identification, recruitment, and registration. The study is expected to commence in Q1 or Q2, 2020 and continue till Q4, 2025. However, the actual length of time needed will be dependent on the uptake of pembrolizumab in MSI-H/dMMR patients and actual recruitment rate.

Among the MSI-H cancer patient is identified to be potentially eligible, electronic health records (EHR) and medical charts may be used to further determine the eligibility of the patients, particularly regarding medical and treatment histories. Patients who already had an MSI-H/dMMR status determined via prior testing will be identified via EHR and medical records and patients who tests MSI-H/dMMR during the recruitment period will also be identified prospectively. These patients will be consented to be enrolled in the registry once they have received at least one dose of pembrolizumab as part of their clinical management and met other eligibility criteria. Patient selection for MSI/MMR tests will be up to the physician's discretion and clinical relevance. Clinical outcomes of interest as specified in the Objectives will be recorded according to pre-specified and standardized format, along with treatment emergent adverse events (TEAEs) as reported by either the patient or the treating physician. The follow-up of the patients will be at least 1 year from the response date of the patients who respond to pembrolizumab treatment.

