3.4 Exclusion Criteria

- Had a diagnosis of hematologic cancer
- Had a diagnosis of CRC
- Already deceased at the time of identification
- Had received checkpoint inhibitors prior to the index diagnosis
- Have or had other primary malignancies

VEAP ID NO: 8439

Epidemiology No.: EP05026.058

4 Variables and Epidemiological Measurements

Data collection in this study will be based a combination of primary and secondary data. Briefly, leveraging the existing EHR systems in each of the cancer centers, if available, information on MSI/MMR testing results and previous medical history and selective baseline clinicopathological characteristics of the study population at enrollment will be extracted. Information that cannot be collected from the EHR system will be extracted from medical charts by trained medical chart extractors. Treatment history, clinical outcomes, and TEAEs following the administration of pembrolizumab will be collected by study staff prospectively.

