4.2 Outcomes

This study will capture both clinical and safety outcomes for each participating patient. All investigators will be requested to use Response Evaluation Criteria in Solid Tumors (RECIST) 1.1 and/or a disease-specific tumor response measurement that are commonly used and accepted for determining tumor responses. The primary clinical outcome is tumor response, which will be categorized into complete response (CR), partial response (PR), progressive disease (PD), and stable disease (SD). The tumor responses will be determined by the investigators who treat the cancer patient, subsequent to an investigators' meeting to reiterate the essential elements to standardize the diagnostic criteria. Date of assessment and the basis of assessment will be captured. The assessment of tumor response will be performed as in routine clinical setting without a study-specified visit schedule. Death is also a clinical outcome and will be captured during the study period. With the collected tumor response and death information, objective response rate (ORR) can be derived. Duration of response (DoR) will also be captured among the responders. Specific definitions of these endpoints are provided in the Statistical Analysis Plan section (section 9). Survival information for both responders and non-responders will be collected periodically from medical records, contact through site investigators or from Taiwan death registry for up to two years from end of follow up.

Safety information regarding TEAEs will be recorded as reported by the patients and/or the treating physicians in course of routine clinical care, without further prompting. TEAEs are AEs that occur sequent to the first administration of the first dose of pembrolizumab. Definitions for AE and SAE are provided in section 7. The severity of

Protocol/Amendment No.: 1.1 (14 Sep 2019)

VEAP ID NO: 8439

Epidemiology No.: EP05026.058

the TEAEs will be assessed and determined according to the National Cancer Institute (NCI) Common Terminology Criteria for Adverse Events (CTCAE) version 5 severity grading.

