4.3 Covariates

- Baseline demographic characteristics, such as
 - o Age
 - o Gender
 - Smoking
- Baseline clinicopathological characteristics, such as
 - o Eastern Cooperative Oncology Group (ECOG) status
 - o Laboratory test results, including MSI/MMR status
 - o Cancer-related medical history prior to enrollment into the study
 - Diagnosis of cancer
 - Histology
 - Treatment history
 - Stage of cancer
 - Any disease specific categorizations (e.g. Child-Pugh classification, castrate resistance, etc.)
 - Comorbidities
 - Vital signs
 - Height
 - Weight
 - Blood pressure
 - Heart rate
- Concomitant medications during study period

Protocol/Amendment No.: 1.1 (14 Sep 2019)

VEAP ID NO: 8439

Epidemiology No.: EP05026.058

5 Study Flow Chart

Table 1. Study flow chart

		Observation/Follow-up		
Study Period	Screening/identification	Baseline (at enrollment)	Treatment visit(s) ^a	Assessment of clinical outcomes ^b
Potential patients identified through medical records	X			
Inclusion/Exclusion Criteria	X	X		
Informed Consent	X			
MSI/MMR status determination	X			
Demographic characteristics as described in section 4		X		
Clinicopathological characteristics as described in section 4		X		X
Vital signs as described in section 4		X	X	X
Concomitant medications		X	X	
Tumor response as described in section 4				X
TEAEs			X	X

Visits are according to real-world routine clinical practice. There are no protocol-specified schedules for these visits. The "study visits" indicate time points at which data is being collected from the patient or the physician.

b Typically, the assessment visit (with imaging, etc.) occurs approximately 2-3 months after the initial treatment in Taiwan

VEAP ID NO: 8439

Epidemiology No.: EP05026.058

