6.1.1 Administrative Procedures

6.1.1.1 MSI-H or dMMR identification

In collaboration with investigators at selective major cancer centers in Taiwan, we will identify eligible patients to be enrolled into the study through a combination of proactive identification and review of EHR and medical records. Medical records of identified patients will be reviewed to confirm prior specific MSI/MMR testing or NGS testing and MSI-H/dMMR status. Patients who did not have prior testing will be included if they have confirmed MSI-H status through MSI/MMR tests during the study period as advised by their physician. Patient selection for MSI/MMR tests will be up to the physician's discretion and clinical relevance. Patients will likely receive PCR-based tests performed by the hospital pathology department or as per other standard institutional processes (third party). Once a patient is confirmed to have MSI-H, and prescribed by the treating physician to receive pembrolizumab, the patient's EHR and/or medical charts will be further reviewed to ensure that the patient meets all inclusion and exclusion criteria. Once the eligibility is confirmed, the patient will then be enrolled in the study.

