6.1.1.4 Treatment information

Information on treatment with pembrolizumab per the treating physician's discretion in routine clinical practice will be collected and recorded by the study investigators/staff during the study period. The start and stop dates for the administration of pembrolizumab and number of cycles given to the patient will be recorded. If dose modification is made during the course of treatment, the date will be recorded, along with the reason(s) for the modification. In addition, during the study period, use of cancer-related concomitant medications will also be recorded by the investigator of study staff.

Spontaneous, patient and/or investigator-reported TEAEs within the study follow up period will be recorded by the study investigator/staff per the specifications in section 7. The study investigators will determine the severity of the TEAEs based on the NSCI CTCAE v5 severity grading.

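### TEAEs are counted from the first dose, but collection is described from enrolment with no look-back, so early non-serious, unrelated events may be under-counted and early response and progression dates lost

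*Protocol*

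**What the plan says.** **Start of the risk window.** Protocol section 4.2: "TEAEs are AEs that occur sequent to the first administration of the first dose of pembrolizumab". Section 9.1.2 also starts PFS and OS at the first dose.

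**Point of entry.** Section 3.2: "These patients will be consented to be enrolled in the registry once they have received at least one dose of pembrolizumab". Section 3.3 makes receipt of a dose an inclusion criterion. Neither section caps the number of doses or the time since the first one. Section 6.1.1.1 describes entry differently: records are reviewed, and the patient is then enrolled, once the patient has been "prescribed by the treating physician to receive pembrolizumab".

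**Collection of events and outcomes.** The opening paragraph of section 4: "Treatment history, clinical outcomes, and TEAEs following the administration of pembrolizumab will be collected by study staff prospectively". Section 6.1.1.4 says that "TEAEs within the study follow up period will be recorded by the study investigator/staff", and section 4.2 says that they are taken as reported "in course of routine clinical care, without further prompting".

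**Use of existing records.** Section 4 says that "information on MSI/MMR testing results and previous medical history and selective baseline clinicopathological characteristics of the study population at enrollment will be extracted". The baseline list in section 6.1.1.3 names demographics, vital signs, ECOG score, test results, cancer history and comorbidity. In Table 1 (section 5), the row "Tumor response as described in section 4" is marked only at outcome assessment. The TEAE row is marked at treatment visits and outcome assessment. Neither is marked at screening or baseline.

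**The concern.** The numerator and the denominator of the safety tables do not cover the same time. Each enrolled patient is at risk of a TEAE from the first dose, but the collection described begins when the patient enters the registry, at least one dose later. Section 9.1.2 then reports TEAE frequencies over the study population by system organ class and worst grade. An event that began and resolved between first dose and enrolment belongs in those tables by definition, yet has no stated way into the data unless another rule brings it in.

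The same interval matters for efficacy. A response first seen before enrolment may be dated at the first assessment after it, which would shorten duration of response (DoR). A progression before enrolment may be missed or dated late, which would lengthen PFS.

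A statistical analysis plan cannot repair this afterwards, because data that were never collected cannot be analysed. The biases and limitations discussed in sections 9.2.1 and 9.2.2 do not include this interval.

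**Working it through.** **Step 1. Is there a look-back anywhere?**

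| Item | Stated use of existing records | Place |
|---|---|---|
| MSI/MMR results, medical history, baseline characteristics | Yes | Sections 4, 6.1.1.3 |
| Pembrolizumab use, including dose modifications and reasons | Yes, EHR as supplement | Section 4.1 |
| Survival | Yes, medical records and death registry | Sections 4.2, 6.1.4 |
| SAEs, deaths and non-serious adverse reactions known to the investigator | Reportable after use of the drug, not tied to enrolment; study-product events go into the study database | Section 7.1.1, Table 2 note [2] |
| Other TEAEs from first dose to enrolment | None stated | – |
| Tumor assessments from first dose to enrolment | None stated | – |

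Where the protocol wants records to supplement prospective data, it says so. It does not say so for the last two rows. One consequence: a dose modification made before enrolment can be recovered with its reason under section 4.1, while the TEAE behind it has no stated look-back of its own. Section 9.1.2 nevertheless tabulates TEAEs leading to dose modification.

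**Step 2. Can the lag be long?** No limit is set. Section 3.1 admits patients whose MSI-H/dMMR status was known before study initiation, and nothing prevents such a patient from being well into treatment. Section 6.1.1.1 suggests a short lag but sets no bound either.

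**Step 3. Size for TEAEs (illustration only).** The protocol gives no lag and no onset times. Its only precision figure, a 19% half-width at N = 20 and ORR 20%, reproduces as the exact interval, (43.7% − 5.7%)/2 = 19.0%, but has no bearing here. Assume exponential onset with median m and a lag g:

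share of first onsets before enrolment, f = 1 − 0.5^(g/m)

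Take an event that truly occurs in 6 of 20 patients (assumed). If nothing is recovered, the recorded number is 6 × (1 − f).

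| Lag g | m = 6 weeks: f | Recorded of 6 | m = 12 weeks: f | Recorded of 6 |
|---|---|---|---|---|
| 3 weeks | 29% | 4.2 | 16% | 5.0 |
| 6 weeks | 50% | 3.0 | 29% | 4.2 |
| 12 weeks | 75% | 1.5 | 50% | 3.0 |

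These are upper bounds on the loss for the assumed g and m. They ignore the section 7.1.1 route, and events still present or recurring after enrolment.

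**Step 4. PFS (illustration only).** Section 3.1 gives a non-CRC median PFS of 5.4 months. With exponential times, the share of PFS events before a lag g is 1 − 2^(−g/5.4): 12.0% at 1 month, 22.6% at 2 and 32.0% at 3. These are underlying event times. Progression is documented at assessments, usually first at 2-3 months (Table 1 note b, section 6.1.4), so few documented progressions precede a short lag.

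**Step 5. ORR.** Two mechanisms pull in opposite directions.

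- A response gained and lost before enrolment would be missed, which lowers ORR.
- Section 3.4 excludes patients already dead at identification, which raises it. With the stated non-CRC median OS of 13.4 months, exponential times, and all early deaths assumed to be non-responders who never enter, the apparent ORR is the true ORR × 2^(g/13.4). A true 20% then appears as 20.7% at a lag of 0.7 months and 23.4% at 3 months.

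The net direction is not determined.

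**The case against.** A reader might infer that everything before enrolment is excluded. The protocol does not say that. The sentence in section 4 covers events after administration of the drug, not after enrolment. It also applies the word for prospective collection to treatment history, although section 6.1.1.3 takes cancer treatment history from records. The word may therefore describe how staff record data, not a cut-off for onset. Table 1 is imperfect evidence too: it has no row for pembrolizumab exposure or survival, yet both are collected. Section 7.1.1 covers serious events, deaths and non-serious adverse reactions once the investigator knows of them, whatever the enrolment date. That supplies most of the serious and drug-related categories in section 9.1.2.

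All of this stands, and it narrows the point. What remains is that non-serious events judged unrelated have no stated route for the interval, although section 9.1.2 reports all TEAEs. The start of the follow-up period in section 6.1.1.4 is also undefined, so sites could reasonably differ on whether earlier events count.

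For tumor response the objection is stronger. With first scans usually at 2-3 months, a short lag loses few assessments. A response still present at enrolment would be seen later, so its onset date suffers more than its being counted.

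**Conclusion.** The mismatch is in the text and should be corrected. The TEAE definition opens at the first dose, entry comes at least one dose later with no limit, and no look-back is provided for TEAEs or tumor assessments. Followed as written, the plan can bias the all-TEAE frequencies low, mainly through early non-serious events judged unrelated. For efficacy, the risk is a misdated response onset (hence DoR) and a missed early progression date (hence PFS), chiefly when the lag exceeds the usual 2-3 months to first assessment.

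The size cannot be computed. The range of 16% to 75% rests on assumed lags of 3 to 12 weeks, assumed median onsets of 6 and 12 weeks, exponential onset and no recovery. It should not be read as the expected loss. Nor should a reader infer that ORR is under-counted: the documents leave its direction open.

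**What to change.** - In section 4 and the Baseline column of Table 1, add extraction from EHR and charts of TEAEs and tumor assessments from first dose to enrolment, flagged as retrospective.
- Record the interval from first dose to enrolment for each patient.
- In section 9.1.2, tabulate TEAEs from the first dose and show the retrospective part separately.
- Reconcile the point of enrolment in sections 3.2 and 3.3 with section 6.1.1.1. The look-back itself does not require earlier consent, and section 3.3 makes at least one dose a condition of entry.

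The cost is small: additional CRF fields, two entries in Table 1 and some abstraction time for 20 patients. Section 4 already plans for chart extractors, and section 6.1.1.3 says that the CRF is still to be developed. The drawback is that adverse events taken from records may be less complete than those collected prospectively; the flag and the separate display make that visible.

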4.1 Exposure

The primary "exposure" variable in this study is the use of pembrolizumab. Information on pembrolizumab use will be collected primarily through prospective registry via a prespecified, standardized case report form (CRF), supplemented with EHR if needed and appropriate. Start and stop dates, number of cycles, total dose, and any dose modification and reason(s) for the modification will also be collected.

4.2 Outcomes

This study will capture both clinical and safety outcomes for each participating patient. All investigators will be requested to use Response Evaluation Criteria in Solid Tumors (RECIST) 1.1 and/or a disease-specific tumor response measurement that are commonly used and accepted for determining tumor responses. The primary clinical outcome is tumor response, which will be categorized into complete response (CR), partial response (PR), progressive disease (PD), and stable disease (SD). The tumor responses will be determined by the investigators who treat the cancer patient, subsequent to an investigators' meeting to reiterate the essential elements to standardize the diagnostic criteria. Date of assessment and the basis of assessment will be captured. The assessment of tumor response will be performed as in routine clinical setting without a study-specified visit schedule. Death is also a clinical outcome and will be captured during the study period. With the collected tumor response and death information, objective response rate (ORR) can be derived. Duration of response (DoR) will also be captured among the responders. Specific definitions of these endpoints are provided in the Statistical Analysis Plan section (section 9). Survival information for both responders and non-responders will be collected periodically from medical records, contact through site investigators or from Taiwan death registry for up to two years from end of follow up.

Safety information regarding TEAEs will be recorded as reported by the patients and/or the treating physicians in course of routine clinical care, without further prompting. TEAEs are AEs that occur sequent to the first administration of the first dose of pembrolizumab. Definitions for AE and SAE are provided in section 7. The severity of

Protocol/Amendment No.: 1.1 (14 Sep 2019)

VEAP ID NO: 8439

Epidemiology No.: EP05026.058

the TEAEs will be assessed and determined according to the National Cancer Institute (NCI) Common Terminology Criteria for Adverse Events (CTCAE) version 5 severity grading.

4.3 Covariates

- Baseline demographic characteristics, such as
 - o Age
 - o Gender
 - Smoking
- Baseline clinicopathological characteristics, such as
 - o Eastern Cooperative Oncology Group (ECOG) status
 - o Laboratory test results, including MSI/MMR status
 - o Cancer-related medical history prior to enrollment into the study
 - Diagnosis of cancer
 - Histology
 - Treatment history
 - Stage of cancer
 - Any disease specific categorizations (e.g. Child-Pugh classification, castrate resistance, etc.)
 - Comorbidities
 - Vital signs
 - Height
 - Weight
 - Blood pressure
 - Heart rate
- Concomitant medications during study period

Protocol/Amendment No.: 1.1 (14 Sep 2019)

VEAP ID NO: 8439

Epidemiology No.: EP05026.058

5 Study Flow Chart

Table 1. Study flow chart

		Observation/Follow-up		
Study Period	Screening/identification	Baseline (at enrollment)	Treatment visit(s) ^a	Assessment of clinical outcomes ^b
Potential patients identified through medical records	X			
Inclusion/Exclusion Criteria	X	X		
Informed Consent	X			
MSI/MMR status determination	X			
Demographic characteristics as described in section 4		X		
Clinicopathological characteristics as described in section 4		X		X
Vital signs as described in section 4		X	X	X
Concomitant medications		X	X	
Tumor response as described in section 4				X
TEAEs			X	X

Visits are according to real-world routine clinical practice. There are no protocol-specified schedules for these visits. The "study visits" indicate time points at which data is being collected from the patient or the physician.

b Typically, the assessment visit (with imaging, etc.) occurs approximately 2-3 months after the initial treatment in Taiwan

VEAP ID NO: 8439

Epidemiology No.: EP05026.058

6 STUDY PROCEDURES

6.1 Study Procedures

The study design (Figure 3 in section 3) and study flow chart (Table 1 in section 5) summarize the study procedures to be performed at each visit. Individual study procedures are described in detail below. It may be necessary to perform additional evaluations/testing by the Sponsor for reasons related to subject safety.

6.1.1 Administrative Procedures

6.1.1.1 MSI-H or dMMR identification

In collaboration with investigators at selective major cancer centers in Taiwan, we will identify eligible patients to be enrolled into the study through a combination of proactive identification and review of EHR and medical records. Medical records of identified patients will be reviewed to confirm prior specific MSI/MMR testing or NGS testing and MSI-H/dMMR status. Patients who did not have prior testing will be included if they have confirmed MSI-H status through MSI/MMR tests during the study period as advised by their physician. Patient selection for MSI/MMR tests will be up to the physician's discretion and clinical relevance. Patients will likely receive PCR-based tests performed by the hospital pathology department or as per other standard institutional processes (third party). Once a patient is confirmed to have MSI-H, and prescribed by the treating physician to receive pembrolizumab, the patient's EHR and/or medical charts will be further reviewed to ensure that the patient meets all inclusion and exclusion criteria. Once the eligibility is confirmed, the patient will then be enrolled in the study.

